APPENDIX 4 WOMEN OF CHILDBEARING POTENTIAL DEFINITIONS AND METHODS OF CONTRACEPTION

DEFINITIONS

Woman of Childbearing Potential (WOCBP)

A woman is considered fertile following menarche and until becoming post-menopausal unless permanently sterile. Permanent sterilization methods include hysterectomy, bilateral salpingectomy, and bilateral oophorectomy.

Women in the following categories are not considered WOCBP

- Premenarchal
- Premenopausal female with 1 of the following:
 - Documented hysterectomy
 - Documented bilateral salpingectomy
 - Documented bilateral oophorectomy

Note: Documentation can come from the site personnel's review of the participant's medical records, medical examination, or medical history interview.

- Postmenopausal female
 - A postmenopausal state is defined as 12 months of amenorrhea in a woman over age 45 years in the absence of other biological or physiological causes. In addition, females under the age of 55 years must have a serum follicle stimulating hormone, (FSH) level > 40 mIU/mL to confirm menopause.

Note: Females treated with hormone replacement therapy, (HRT) are likely to have artificially suppressed FSH levels and may require a washout period in order to obtain a physiologic FSH level. The duration of the washout period is a function of the type of HRT used. The duration of the washout period below are suggested guidelines and the investigators should use their judgement in checking serum FSH levels.

- 1 week minimum for vaginal hormonal products (rings, creams, gels)
- 4 week minimum for transdermal products
- 8 week minimum for oral products

Other parenteral products may require washout periods as long as 6 months. If the serum FSH level is > 40 mIU/ml at any time during the washout period, the woman can be considered postmenopausal.

CONTRACEPTION GUIDANCE FOR FEMALE PARTICIPANTS OF CHILD BEARING POTENTIAL

One of the highly effective methods of contraception listed below is required during study duration and until the end of relevant systemic exposure, defined as 1 days after the end of study treatment, plus 30 days

Local laws and regulations may require use of alternative and/or additional contraception methods.

Highly Effective Methods That Are User Independent

- Nonhormonal IUDs, such as ParaGard ®
- Bilateral tubal occlusion
- Vasectomized partner

A vasectomized partner is a highly effective contraception method provided that the partner is the sole male sexual partner of the WOCBP and the absence of sperm has been confirmed. If not, an additional highly effective method of contraception should be used.

- Complete Sexual abstinence

Sexual abstinence is considered a highly effective method only if defined as refraining from heterosexual intercourse during the entire period of risk associated with the study treatment. The reliability of sexual abstinence needs to be evaluated in relation to the duration of the study and the preferred and usual lifestyle of the participant.

- Complete abstinence is an acceptable form of contraception for all study drugs and must be used throughout the duration of the study treatment (plus 5 half-lives of the investigational drug plus 30 days)
- It is not necessary to use any other method of contraception when complete abstinence is elected.
- WOCBP participants who choose complete abstinence must continue to have pregnancy tests, as specified in [Section 2](#).
- Acceptable alternate methods of highly effective contraception must be discussed in the event that the WOCBP participants chooses to forego complete abstinence

Unacceptable Methods of Contraception

- Periodic abstinence (calendar, symptothermal, post-ovulation methods)
- Withdrawal (coitus interruptus).
- Spermicide only
- Lactation amenorrhea method (LAM)

- Progestogen-only oral hormonal contraception, where inhibition of ovulation is not the primary mechanism of action
- Hormonal methods of contraception including oral contraceptive pills containing combined estrogen + progesterone, vaginal ring, injectables, implants and intrauterine devices (IUDs) such as Mirena ®
- Intrauterine hormone-releasing system (IUS)
- Diaphragm with spermicide
- Cervical cap with spermicide
- Vaginal Sponge with spermicide
- Male or female condom with or without spermicide*. Male and female condoms cannot be used simultaneously

*** REFERENCES FOR THE USE OF CONDOMS WITH SPERMICIDE.**

Kestelman P. et. al., Efficacy of the Simultaneous Use of Condoms and Spermicides Family Planning Perspectives. Vol 23 (5); October 1991.

CONTRACEPTION GUIDANCE FOR MALE PARTICIPANTS WITH PARTNER(S) OF CHILD BEARING POTENTIAL.

Male participants with female partners of childbearing potential are eligible to participate if they agree to the following during the treatment and until the end of relevant systemic exposure.

- Inform any and all partner(s) of their participation in a clinical drug study and the need to comply with contraception instructions as directed by the investigator.
- Male participants are required to use a condom for study duration and until the end of relevant systemic exposure defined as 91 days after the end of treatment in the male participant.
- Female partners of males participating in the study to consider use of effective methods of contraception until the end of relevant systemic exposure, defined as 91 days after the end of treatment in the male participant.
- Male participants with a pregnant or breastfeeding partner must agree to remain abstinent from penile vaginal intercourse or use a male condom during each episode of penile penetration during the treatment and until 91 days after the end of treatment.
- Refrain from donating sperm for the duration of the study treatment and for 91 days after the end of treatment.

COLLECTION OF PREGNANCY INFORMATION

Guidance for collection of Pregnancy Information and outcome of pregnancy on the Pregnancy Surveillance Form is provided in [Section 9.2.5](#) and the Appendix for Adverse Events and Serious Adverse Events Definitions and procedures for Evaluating, Follow-up and Reporting

7.6.9	Oxygen Saturation	24
7.8	Pharmacokinetics	24
8	CONVENTIONS	25
8.1	Safety Data Conventions	25

8.2	Baseline Measurements	25
8.3	Multiple Measurements	25
8.4	Pharmacokinetic Summaries	26
9	CONTENT OF REPORTS	26

A series of horizontal black bars of varying lengths, likely representing a barcode or a series of data markers. The bars are arranged vertically and are of different widths, creating a pattern of alternating black and white spaces.

Schedule of Analyses:

There is no Data Monitoring Committee (DMC) planned for this study. Occurrence of significant safety events will be submitted for review to the independent DMC that monitors the ongoing phase 2b study, evaluating the safety, tolerability and effectiveness of BMS-986231 in a population of acute decompensated heart failure patients (NCT03016325)¹.

The final analysis will be performed following the database lock after all subjects have completed the study. No interim analyses will be performed

2 STUDY DESCRIPTION

2.1 Study Design

This is a multi-center, randomized, cross-over, placebo and active-controlled, double-blind, study of continuous 5-hour intravenous (IV) infusions of BMS-986231 in patients with heart failure and reduced ejection fraction (HFrEF). The trial is designed to evaluate the effects of BMS-986231 on systolic and diastolic parameters measured by echocardiography.

A cross-over design will be implemented in this trial; every subject will be exposed to each of the 3 interventions (BMS-986231, Nitroglycerin (NTG) and placebo) in 3 treatment periods. Each treatment period will include one intervention occurring via 5-hour infusion, followed by a washout period of at least 7 days, but no more than 4 weeks.

42 study participants will be randomized to receive BMS-986231, NTG, and placebo, in one of the 6 possible sequences.

NTG, BMS-986231 and placebo will be administered as a 5-hours infusion according to an uptitration schedule, which is achieved by an increase in the infusion flow rate. All three interventions (NTG, BMS-986231 and placebo) will have the same flow rate: 5 mL/H for 10 min, followed by 10 mL/H for 10 minutes then 20 mL/H for the rest of the infusion.

[figure not shown]
The corresponding doses of the active study medications will be:

- NTG: 20 $\mu\text{g}/\text{min}$ for 10 min, followed by 40 $\mu\text{g}/\text{min}$ for 10 min, followed by 80 $\mu\text{g}/\text{min}$ for the rest of the 5-hour infusion;
- BMS-986231: 3 $\mu\text{g}/\text{kg}/\text{min}$ for 10 min, followed by 6 $\mu\text{g}/\text{kg}/\text{min}$ for 10 min, followed by 12 $\mu\text{g}/\text{kg}/\text{min}$ for the rest of the 5-hour infusion.

In case of a decrease in systolic blood pressure, an algorithm will be used to down-titrate /interrupt or discontinue the study drug infusion (see protocol [Section 7.4](#)).

The study design schematic is presented in Figure [2.1-1](#).

Figure 2.1-1: Study Design

*Wash-out period will be at least 7 days and no more than 4 weeks

Screening

Screening for inclusion in the study will be performed up to 4 weeks before the first treatment day. Screening will assess the eligibility criteria including assessment of ejection fraction, suitability of echocardiography windows and image quality. After screening, study participants will be enrolled in the study according to their eligibility as per the inclusion and exclusion criteria, and will be randomized to 1 of the 6 sequences that will be conducted in parallel.

Treatment day (Day 1 of each period)

Study participants will be admitted to the study facility on the treatment day, which will be Day 1 of each of the three periods. Assessment of vital signs and laboratory tests will be performed pre-dose. In each treatment day, blood pressure and heart rate should be within the inclusion / exclusion criteria limits, and no atrial fibrillation or atrial flutter should be present in order to start the study treatment. The study drug infusion could start without waiting for the results of the laboratory assessments done in the morning of the treatment day at the study facility if the following criteria are met:

- The results of the laboratory assessment at screening / previous period are within ranges compatible with inclusion/exclusion criteria,
- The study participant was medically stable without change in medication since the screening visit / previous period.

If the laboratory tests (e.g. electrolytes, serum creatinine, eGFR, hemoglobin, transaminases) in the morning prior to the infusion are not within inclusion and exclusion criteria limits, the study drug will be discontinued after consultation with the medical monitor. The abnormalities should be corrected before the next treatment period.

Physical examinations, vital sign measurements, 12-lead electrocardiograms (ECG), echocardiography, whole body bioimpedance and pulse wave analysis (non-invasive central aortic blood pressure) will be performed at selected times throughout the dosing interval. Participants will be closely monitored for adverse events throughout the study. Blood samples will also be collected at selected intervals after start of study drug administration for pharmacokinetic (PK) analysis.

Discharge

Study participants will remain in the study facility for approximately 3.5 hours post-dose and discharged on the same day, unless the investigator and the study team consider that an overnight stay is warranted. Same-day discharge is allowed if the following conditions are met:

- in the opinion of the investigator an overnight stay is not warranted,
- there is no hypotension after mobilization and
- none of the following events occurred during the study drug infusion: prolonged hypotension, symptoms of hypotension, new onset of sustained arrhythmia requiring pharmacologic or other interventions, any other events of concern e.g. chest pain suggestive of ischemia.

2.2 Treatment Assignment

This study will use Interactive Response Technology (IRT): All participants will be centrally randomized using an Interactive Response Technology (IRT). Subjects will be randomized using IRT in a 1:1:1:1:1:1 ratio to one of six sequences, as shown in Figure 2.1-1, with block size of six, to ensure the number of subjects randomized to each sequence remains balanced.

Study treatment will be dispensed at the study visits as listed in Schedule of Activities (Protocol [Section 2](#)).

Enrolled participants, including those not dosed, will be assigned sequential participant numbers starting with 00001, (e.g., 00001, 00002, 00003.... 00010). Those enrolled participants meeting inclusion and exclusion criteria will be eligible to be randomized. Randomization ID numbers will be assigned prior to dosing. Subjects who are re-enrolled (Protocol [Section 6.4](#)) will be assigned a new participant number. An estimated 52 subjects will be screened in order to randomize 42 subjects. Further details are provided in [Section 5](#).

Participants will not be replaced if they are discontinued from the study.

2.3 Blinding and Unblinding

Blinding of treatment assignment is critical to the integrity of this clinical study. However, in the event of a medical emergency or pregnancy in an individual participant in which knowledge of the investigational product is critical to the participant's management, the blind for that participant may be broken by the investigator. The participant's safety takes priority over any other considerations in determining if a treatment assignment should be unblinded.

Before breaking the blind of an individual participant's treatment, the investigator should determine that the unblinded information is necessary, i.e., that it will alter the participant's immediate management. In many cases, particularly when the emergency is clearly not related to the investigational product, the problem may be properly managed by assuming that the participant is receiving active product. It is highly desirable that the decision to unblind treatment assignment be discussed with the Medical Monitor, but the investigator always has ultimate authority for the decision to unblind. The Principal Investigator should only call in for emergency unblinding AFTER the decision to discontinue the participant has been made.

For this study, the method of unblinding for emergency purposes is via the Interactive Response Technology (IRT) system. For information on how to unblind in an emergency, consult the IRT manual.

In cases of accidental unblinding, contact the Medical Monitor and ensure every attempt is made to preserve the blind.

Any request to unblind a participant for non-emergency purposes should be discussed with the Medical Monitor.

The Bioanalytical Sciences section or its designate may be unblinded to the randomized treatment assignments, in order to minimize unnecessary assays of samples from subject during

the placebo treatment period. Likewise, the Biotransformation section or its designate may be unblinded, if metabolite profiling work is conducted.

In certain circumstances, a pharmacokineticist or designate(s) in Clinical Pharmacology and Pharmacometrics, biostatistician(s) and programmer(s) at BMS, or designee, may be unblinded in order to prepare preliminary summaries of PK and safety data, as needed. These summaries will not reveal individual subjects' treatment sequence assignments.

2.4 Protocol Amendments

This statistical analysis plan (SAP) is based on the revised protocol version 02, which incorporates Amendment 02, dated 01-Sep-2017.

2.5 Data Monitoring Committee and Other External Committees

There is no Data Monitoring Committee (DMC) planned for this study. The occurrence of significant safety events will be submitted for review to the independent DMC that monitors the ongoing phase 2b study CV013011, evaluating the safety, tolerability and effectiveness of BMS-986231 in a population of acute decompensated heart failure patients (NCT03016325).

The executive committee will be a small body comprised of academic leaders. The executive committee will provide advice on overall design, study endpoints and recommendations for study sites, and will review results from final analyses with Sponsor.

3 OBJECTIVES

3.1 Primary

The primary objective is to evaluate the effects of BMS-986231 on the left ventricular (LV) systolic function by SVI assessed by echocardiography compared to placebo.

3.2 Secondary

Secondary objectives include the following:

- Evaluate the effects of BMS-986231 on the left ventricular (LV) systolic function by SVI assessed by echocardiography compared to nitroglycerin (NTG).
- Evaluate the effects of BMS-986231 on selected other left ventricular systolic and diastolic indices compared to placebo and NTG:
 - LV ejection fraction
 - Mean LV power index
 - Diastolic function
 - LV global longitudinal strain

Term	Percentage
GMOs	~95%
Organic	~90%
Natural	~85%
Artificial	~75%
Organic	~70%
Natural	~65%
Artificial	~60%
Organic	~55%
Natural	~50%
Artificial	~45%
Organic	~40%
Natural	~35%
Artificial	~30%

4 ENDPOINTS

4.1 Primary Endpoints

[figure not shown]
The primary endpoint is the Mean SVI derived from the velocity time integral at the left ventricular outflow tract (LVOT VTI) at the end of the 5-hours infusion of BMS-986231, versus placebo.

4.2 Secondary Endpoints

Secondary endpoints include the following:

- Mean SVI derived from LVOT VTI at the end of the 5-hours infusion of BMS-986231, versus NTG.
- Mean LVEF, computed by Simpson's method at the end of the 5-hours infusion of BMS-986231, versus placebo and NTG.
- Mean cardiac power index at the end of the 5-hours infusion of BMS-986231, versus placebo and NTG.
- Mean Diastolic indices: E/A, annular e' velocity, and E/ e' ratio at the end of the 5-hours infusion of BMS-986231, versus placebo and NTG.
- Mean LV global longitudinal strain, computed using STE at the end of the 5-hours infusion of BMS-986231, versus placebo and NTG.

Term	Percentage
GMOs	~10%
Organic	~25%
Natural	~35%
Artificial	~85%
Organic	~20%
Natural	~30%
Artificial	~40%
Organic	~25%
Natural	~35%
Artificial	~50%

4.4 Pharmacokinetic Endpoints

- Pharmacokinetic endpoints include the Plasma concentrations of BMS-986231 and its metabolites

5 SAMPLE SIZE AND POWER

In a review of stroke volumes and SVIs from the literature, baseline SVI generally ranged from 30-40 mL/m², with inter-individual standard deviation (SD) of approximately 25 – 35% of the mean. Likewise, SV values generally ranged from 50-70 mL, with inter-individual SD of approximately 25 – 35% of the mean. Results from these studies also suggest intra-individual correlations in the range of 0.6 – 0.8.

Sample size calculations assume baseline SVI of approximately 30 mL/m², with placebo values consistent with baseline, an increase of 15% from baseline, relative to placebo, as meaningful (e.g. 4.5 mL/m²), an inter-individual SD of 10 mL/m², and intra-individual correlations for the difference between placebo and HNO of 0.7. Using these assumptions, approximately 36 subjects with data from treatment periods being compared will be required to achieve a power of 90%, with a type I error probability of 0.05 (2-sided). In order to address the potential for missing data arising from dropout, an allowance of 15% subjects will be included, with a resulting target sample size of 42 subjects to be randomized. An estimated 52 subjects will be screened, in order to randomize 42 subjects. Sample sizes are calculated based on method IV from Mehrotra², which compares post baseline values, adjusting for the differences in the baseline value. The blinded SVI data will be reviewed after 50% of the planned treated subjects have completed treatment. BMS will consider re-estimating the sample size based on the observed SD. The review of SVI data will be repeated if necessary.

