10 STATISTICAL CONSIDERATIONS

10.1 Sample Size Determination

Based on a review of stroke volumes and stroke volume indices from the literature^{36,37}, baseline stroke volume index generally ranged from 30-40 mL/m², with inter-individual SD of approximately 25 – 35% of the mean. Likewise, SV values generally ranged from 50-70 mL, with inter-individual SD of approximately 25 – 35% of the mean. Results from these studies also suggest intra-individual correlations in the range of 0.6 – 0.8.

Sample size calculations assume baseline SVI of approximately 30 mL/m², with placebo values consistent with baseline, an increase of 15% from baseline, relative to placebo, as meaningful (e.g. 4.5 mL/m²), an inter-individual SD of 10 mL/m², and intra-individual correlations for the difference between placebo and HNO of 0.7. Using these assumptions, approximately 36 subjects with data from treatment periods being compared will be required to achieve a power of 90%, with a type I error probability of 0.05 (2-sided). In order to address the potential for missing data arising from dropout, an allowance of 15% subjects will be included, with a resulting target sample size of 42 subjects to be randomized. Sample sizes are calculated based on method IV from Mehrotra³⁸, which compares post baseline values, adjusting for the differences in the baseline value.

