The mean SVI at the end of 5-hour infusion of BMS-986231 versus Placebo, corresponding standard error, p value, and 95% confidence interval will be calculated by the below SAS code and presented. Considering the sample size is small, the Kenward-Roger degree of freedom is used to adjust the standard error of treatment effect.

```
PROC MIXED DATA=EXAMPLE_DATA;
  CLASS sequence;
  MODEL ydiff TP = sequence xdiff TP / DDFM=KENWARDROGER;
  ESTIMATE 'tau_T - tau_P' intercept 1 xdiff_TP / CL;
  run;
```

SVI will be summarized and listed for all randomized subjects as overall and by treatment.

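### Does the undefined SD in the SAP's blinded sample-size review leave the trial's power unprotected?

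*SAP*

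**What the plan says.** SAP 5 sizes the trial on two nuisance parameters, "an inter-individual SD of 10 mL/m², and intra-individual correlations for the difference between placebo and HNO of 0.7", with a target difference of 4.5 mL/m². The literature review in the same section gives a spread for both. The SD is put at 25 to 35% of a mean of 30 to 40 mL/m². For the correlation, "Results from these studies also suggest intra-individual correlations in the range of" 0.6 to 0.8. Protocol 10.1 uses the same inputs and concludes that "approximately 36 subjects with data from treatment periods being compared will be required to achieve a power of 90" per cent.

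SAP 5 then adds a safeguard: "The blinded SVI data will be reviewed after 50% of the planned treated subjects have completed treatment", and "BMS will consider re-estimating the sample size based on the observed SD". The look may be repeated. No formula is given, and the type of SD is not stated. The protocol's sample-size text does not mention the review, which is an omission and contradicts nothing.

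The primary analysis in SAP 7.5.1 regresses the within-subject BMS-986231 minus placebo difference on sequence and the baseline difference: "MODEL ydiff TP = sequence xdiff TP / DDFM=KENWARDROGER".

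**The concern.** Power in this crossover depends on the SD of the within-subject difference. Before baseline adjustment that is SD × √(2(1 − ρ)), so both the SD and the correlation ρ matter. The only SD that SAP 5 names is the inter-individual one. If that is what gets updated, with ρ kept at 0.7, the review cannot respond to an error in ρ. It would leave the trial at its planned size when ρ is lower than assumed, and it could prompt an unneeded increase when a larger SD comes with a higher ρ. A safeguard meant to protect 90% power would then miss one of the two ways in which that power can be lost.

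**Working it through.** **Inputs.** From SAP 5: difference 4.5 mL/m², SD 10, ρ 0.7 (range 0.6 to 0.8), two-sided alpha 0.05, power 90%, 36 completers, 42 randomized. Half of 42 is 21 subjects at the review. Not in the documents, and therefore assumed: the same-day pre/post correlation r, varied over 0.75, 0.80 and 0.85.

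**The plan's own figure.** SD of the difference = 10 × √(2 × 0.3) = 7.75. A noncentral-t paired calculation gives 34 completers, and power at 36 is 92.3%. The stated 36 is the next multiple of the six sequences, so the plan's figure is reproduced closely enough.

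**Effect of ρ without the covariate (SD 10).**

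| ρ | SD of difference | Completers for 90% | Power at 36 |
|---|---|---|---|
| 0.6 | 8.94 | 44 | 83.5% |
| 0.7 | 7.75 | 34 | 92.3% |
| 0.8 | 6.32 | 23 | 98.6% |

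An update of the inter-individual SD with ρ fixed at 0.7 centres on 34 in all three rows. In simulated blinded reviews of 21 subjects, with a 4.5 effect and nitroglycerin (NTG) set equal to placebo, the mean per-period SD was 10.08, 10.08 and 10.09 for ρ 0.6, 0.7 and 0.8. It does not move with ρ.

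**What an SD review does cover.** The SAP's own SD range runs from 0.25 × 30 = 7.5 to 0.35 × 40 = 14. At ρ 0.7 that moves the completers needed from 20 to 63, a wider span than the 23 to 44 produced by the correlation range.

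**Adding the planned covariate.** Let every cross-period correlation be ρ. Both the outcome difference and the baseline difference have variance 2·SD²(1 − ρ), and their covariance is 2·SD²(r − ρ). The residual variance is therefore 2·SD²(1 − ρ) × [1 − ((r − ρ)/(1 − ρ))²]. With SD 10 and ρ 0.6 the first factor is 80:

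| r | Residual variance | Residual SD | Completers for 90% | Power at 36 |
|---|---|---|---|---|
| 0.75 | 80 × (1 − 0.375²) = 68.75 | 8.29 | 38 | 89% |
| 0.80 | 80 × (1 − 0.5²) = 60.00 | 7.75 | 34 | 92% |
| 0.85 | 80 × (1 − 0.625²) = 48.75 | 6.98 | 28 | 96% |

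At r = 0.80 the residual SD equals the planned 7.75 exactly. The 83.5% figure applies when r is no higher than ρ.

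**Would naming another SD do better?** The natural candidate is the residual SD from a model with subject and period, fitted to the three pre-infusion values and multiplied by √2. The check used 20,000 simulated reviews of 21 subjects with SD 10 and ρ 0.6, and compared the re-estimated number with the baseline-adjusted number actually needed:

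| r | Needed | RMS error, inter-individual SD with ρ 0.7 | RMS error, pre-infusion within-subject SD |
|---|---|---|---|
| 0.75 | 38 | 8.7 | 11.0 |
| 0.80 | 34 | 7.5 | 13.6 |
| 0.85 | 28 | 9.4 | 18.4 |

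At r = 0.80 the within-subject version asks for more than 36 in 79% of reviews, although 34 suffice. If the covariate is ignored, the order reverses: 12.8 against 9.1 for a need of 44.

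Post-infusion values have a different defect. Blinded, they absorb the treatment effect. In the simulated reviews the within-subject SD of a difference averaged 8.51 at ρ 0.7, against a true 7.75.

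**The case for a change.** The best case for a change is that the gap is real and cheap to close. SAP 5 names only an inter-individual SD, that SD carries no information on ρ, and the SAP itself allows ρ as low as 0.6. Writing the quantity down beforehand would also remove any doubt about how the number came to be changed. Without the covariate, a within-subject SD lands closer to the number needed at each of ρ 0.6, 0.7 and 0.8, for both SD 10 and SD 12.

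The reading of the text stands, and so does the unadjusted arithmetic. Two things do not carry over. First, the harm needs a rule that the SAP does not contain: inter-individual SD with ρ frozen at 0.7. If the within-subject SD is meant, neither harm arises. Second, the advantage of the within-subject SD depends on leaving out the covariate that SAP 7.5.1 includes. Once the covariate is in and same-day values correlate more strongly than values from different periods, the advantage reverses in the cases checked at ρ 0.6.

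**Conclusion.** No change follows. The SAP leaves out a detail that the statistician running the review can fill sensibly: the same paragraph sizes the trial from an SD and a correlation, blinded SVI data from all three periods will be to hand, and nothing commits the sponsor to keeping 0.7. Whoever runs the review should look at the variability of the baseline-adjusted difference in SAP 7.5.1, and the present wording permits that.

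Even on the unfavourable reading the exposure is limited. At ρ 0.6, power at 36 is 84% if the covariate gains nothing, and about 89 to 96% for same-day correlations of 0.75 to 0.85. The SD range, which any version of the review addresses, is the larger risk to the sample size. The obvious substitute is not shown to be better under the planned analysis.

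These figures assume normal data, SD 10, equal cross-period correlations, and same-day correlations that the documents do not state. If same-day values correlated no more strongly than values from different periods, the unadjusted figures would apply and the case for spelling out the SD would be stronger. A blinded review on any of these quantities raises no type I error concern here.
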